**3. Look at T1 pre-contrast images/non contrasted images**

- A. Is there new blood?
- B. Are there calcifications?

**4. Look at T2 and/FLAIR images (Note: my preference is for FLAIR images)/non contrasted images**

- A. Most frequently, we look at axial FLAIR images.
- B. Determine RANO – T2/FLAIR lesion response.
- C. Be careful with increase T2/FLAIR from tumor progression vs. treatment effect. Is there increased mass effect? Is there atrophy? Is it in the radiation field?

[figure not shown]
FLAIR

[figure not shown]
T2

Response	Definition
Improved	Signal abnormality decreased
Unchanged	Unchanged compared to prior imaging
Worse	Unequivocal worsening/progression of signal abnormality (due to tumor - make sure this is not due to infection, infarction, demyelination, radiation)
Unable to Assess (UA)	Unable to evaluate non-enhancing lesions because of technical factors

##### 5. Post contrast T1-weighted images/post contrast images

- Look at **two planes**: Axial, Coronal, Sagittal.
- Make sure you are looking at the post contrast scans. Is the nasal mucosa white (post contrast) or the same grey shade as the brain parenchyma (non contrasted)?

[figure not shown]

[figure not shown]

**T1 pre contrast**

**T1 post contrast**

- C. Pick target lesion.
  - i. Some lesions are followed quantitatively, some qualitatively.
  - ii. Measurable lesions are those that you COULD follow quantitatively
  - iii. Target lesions are those that you WILL follow quantitatively
  - iv. Only enhancing lesions can be quantitative.
- D. Measurable lesions must have the following criteria:
  - v. Contrast enhancing
  - vi. Clearly defined, bi-dimensionally measurable margins
  - vii. Two perpendicular diameters  $\geq 10\text{mm}$
  - viii. If slice thickness + gap is  $>5\text{mm}$ , size threshold is 2 x total
  - ix. Do not include surgical cavity, cyst, or necrotic area
- E. Non-measurable lesions meet the following criteria:
  - x. Less than 1 cm in any diameter (e.g.  $12 \times 8\text{ mm}$ )
  - xi. Poorly defined margin
  - xii. Hemorrhagic or predominantly necrotic
  - xiii. Tumor around a cyst or surgical cavity, unless nodular component  $\geq 10 \times 10\text{ mm}$
- F. Choosing target lesions:
  - xiv. If there is more than one, pick up to 5.
  - xv. Choose the largest lesions.
  - xvi. Should have reproducible measurement.

G. Determine RANO – Target lesion measurement/response

- i. Axial plan is recommended, unless patient has been followed in coronals
- ii. Pick the slice where the lesion is the largest
- iii. Measure the longest diameter (A)
- iv. Next, measure the greatest perpendicular diameter (B)
- v. Calculate the target lesion size - product of the diameters (AXB)
- vi. With multiple target lesions, calculate the sum of the product of the diameters  

$$(SPD) = \text{Area001} + \text{Area002}$$
- vii. Follow-up evaluation:
  - a. Measure the previously defined target lesions bi-dimensionally and calculate the SPD (Note: CR and PR have to be confirmed  $\geq 4$  weeks later; otherwise, it's just SD)
  - b. If apparent PD within 12 weeks of radiation, keep watching. If SPD stable or decreased on next visit, drop baseline value when picking "nadir" to compare against.
  - c. Are there new lesions?

H. RANO – Enhancing non-target lesion response

- i. All non-measurable lesions
- ii. All measurable lesions beyond upper limit of 5
- iii. All other measurable lesions not selected as target lesion

Response	Definition
Complete Response (CR)	All target lesions have completely disappeared. (look out for pseudoresponse)
Partial Response (PR)	SPD decreased by $\geq 50\%$ from baseline value (look out for pseudoresponse)
Stable Disease (SD)	SPD < 50% decrease to < 25% increase
Progressive Disease (PD)	SPD increased by $\geq 25\%$ from nadir value (smallest seen during the trial) (look out for pseudoprogression)
Unable to Assess (UA)	One or more of the target lesions cannot be evaluated because of technical factors

iv. Assessed subjectively

Response	Definition
Complete Response (CR)	All enhancing non-target lesions have disappeared completely
Incomplete Response /Stable Disease (IR/SD)	Enhancing lesions present, and stable or decreased in size compared to prior imaging
Progressive Disease (PD)	Unequivocal progression of enhancing lesions (see below)

Unable to Assess (UA)	Unable to evaluate enhancing lesions because of technical factors
-----------------------	---

- I. Pseudoresponse
  - i. Anti-angiogenic drug effects can look like response
  - ii. Apparent response may appear within 4 weeks
  - iii. This should be confirmed with follow-up imaging 4+ weeks later
- J. Pseudoprogression
  - i. Enhancement that looks like tumor growth but isn't
  - ii. Radiation effect can look like tumor
  - iii. Apparent PD within 12 weeks of RT
  - iv. Call it pseudoprogression (psPD) initially v. Re-evaluate at next imaging visit
  - vi. If further increase, call it PD on the first visit vii. If stable or decreased, psPD is confirmed
  - viii. Do not consider baseline for choosing nadir – looking for progression
  - ix. Still use baseline when looking for response x. New lesions
  - xi. PD within the 12 weeks of completion of chemoradiation can only be assigned if:
    - a. Majority of the new enhancement is outside of the radiation field
    - OR
    - b. Pathologic confirmation of progressive disease (tricky)
    - c. Lesion continues to enlarge

Baseline	Visit 1 (8 weeks)	Visit 2 (16 weeks)	Visit 3 (24 weeks)
100	140 psPD	120 SD	150 → PD 130 → SD 65 → SD 45 → PR

K. RANO – From lesion to timepoint (radiological)

Target Lesions	Enhancing Non-Target Lesions	FLAIR/T2 Lesions	New Lesions	Radiological Timepoint Response
CR	CR	Not worse	No	CR
CR	IR/SD or UA	Not worse	No	PR
PR	Any non-PD or UA	Not worse	No	PR

SD	Any non-PD or UA	Not worse	No	SD
UA	Any non-PD	Not worse	No	UA
PD	Any	Any	Yes/No	PD
Any	PD	Any	Yes/No	PD
Any	Any	Any	Yes	PD
Any	Any	Worse	Yes/No	PD
NA*	CR	Not worse	No	CR
NA*	SD	Not worse	No	SD
NA*	NA**	Not worse	No	No Change
NA* = No target lesions identified at baseline. NA** = No non-target lesions identified at baseline				

L. RANO – Radiological and clinical factors

Overall Visit Response	Definition
CR	
 
• CR by MRI
 
• No steroids above physiological levels
 
• Clinical status stable or improved compared to baseline
 

PR	
 
• PR by MRI
 
• Steroid dose not increased compared to baseline
 
• Clinical status stable or improved compared to baseline
 

SD	
 
• SD by MRI
 
• Steroid dose not increased compared to baseline
 
• Clinical status stable or improved compared to baseline
 

PD	
 
PD by MRI
 
Steroid dose stable or higher compared to visit at which best MRI response was seen
 
Clinical status worsened compared to either baseline or the visit which showed the best MRI response, and not attributable to a non tumor-related cause
 

NC	
 
NC by MRI (possible only if no visible tumor at baseline)
 
Steroid dose not increased compared to baseline
 
Clinical status stable or improved compared to baseline
 

UA	
 
UA by MRI
 
Steroid dose not increased compared to baseline
 
Clinical status stable or improved compared to baseline
 

M. RANO response criteria

	CR	PR	SD	PD
T1-Gd +	None	$\geq 50\% \downarrow$	$< 50\% \downarrow -$ $< 25\% \uparrow$	$\geq 25\% \uparrow^*$
T2/FLAIR	Stable or <math>\downarrow</math>	Stable or <math>\downarrow</math>	Stable or <math>\downarrow</math>	$\uparrow^*$
New Lesion	None	None	None	Present*
Corticosteroids	None	Stable or <math>\downarrow</math>	Stable or <math>\downarrow</math>	NA
Clinical Status	Stable or <math>\uparrow</math>	Stable or <math>\uparrow</math>	Stable or <math>\uparrow</math>	$\downarrow^*$
Requirement for response	all	all	all	Any*

	CR	PR	SD	PD
T1-Gd +	None	$\geq 50\% \downarrow$	$< 50\% \downarrow -$ $< 25\% \uparrow$	$\geq 25\% \uparrow^*$
T2/FLAIR	Stable or <math>\downarrow</math>	Stable or <math>\downarrow</math>	Stable or <math>\downarrow</math>	$\uparrow^*$
New Lesion	None	None	None	Present*
Corticosteroids	None	Stable or <math>\downarrow</math>	Stable or <math>\downarrow</math>	NA
Clinical Status	Stable or <math>\uparrow</math>	Stable or <math>\uparrow</math>	Stable or <math>\uparrow</math>	$\downarrow^*$
Requirement for response	all	all	all	Any*

	CR	PR	SD	PD
T1-Gd +	None	$\geq 50\% \downarrow$	$< 50\% \downarrow -$ $< 25\% \uparrow$	$\geq 25\% \uparrow^*$
T2/FLAIR	Stable or <math>\downarrow</math>	Stable or <math>\downarrow</math>	Stable or <math>\downarrow</math>	$\uparrow^*$
New Lesion	None	None	None	Present*
Corticosteroids	None	Stable or <math>\downarrow</math>	Stable or <math>\downarrow</math>	NA
Clinical Status	Stable or <math>\uparrow</math>	Stable or <math>\uparrow</math>	Stable or <math>\uparrow</math>	$\downarrow^*$
Requirement for response	all	all	all	Any*

N. Additional info to help

- i. Split lesion: measure all and add them together
- ii. Merge: measure the big thing
- iii. If CR by MRI but still on steroids : PR
- iv. If PR by MRI but steroids up : SD
- v. SD by MRI with steroids up (but neurological exam OK): SD for now
  - a. If next visit shows either neurologic or MRI worsening, call PD when the steroids were increased.
- vi. For patients with non-measurable disease only at baseline:
  - a. Cannot have a CR or PR.
  - b. Best response possible is SD.

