### 3.3 Selection of Subjects

Selection of subjects will be completed by meeting the subject eligibility criteria listed in this section.

Inclusion Criteria (answer must be YES to all criteria listed below)

1. Patients must have histologically confirmed diagnosis of WHO grade 4 malignant glioma and radiographic evidence of recurrence or disease progression (as defined by the RANO criteria as a greater than 25% increase in the largest bi-dimensional product of enhancement or a new enhancing lesion, or a significant increase in T2/FLAIR abnormality without another co-morbid cause);
2. Age  $\geq$  18 years;
3. Karnofsky Performance Status  $\geq$  70%;
4. No more than 3 prior progressions;
5. Cohort 1 only: Non-bevacizumab failure, i.e. either no prior bevacizumab or bevacizumab stable/responder, which is defined as stable for at least 6 months from prior treatment with bevacizumab without experiencing a bevacizumab adverse event of special interest (AESI) while on a bevacizumab-containing regimen, such as:
  - a.  $\geq$  grade 3 hypertension not controlled by medication, hypertensive crisis, or hypertensive encephalopathy
  - b.  $\geq$  grade 3 proteinuria that does not resolve or nephrotic syndrome
  - c. Any grade GI perforation
  - d.  $\geq$  grade 3 infusion-related reaction
  - e.  $\geq$  grade 3 wound healing complications
  - f.  $\geq$  grade 3 hemorrhage or any grade CNS hemorrhage or  $\geq$  grade 2 hemoptysis
  - g. Any grade arterial thromboembolic event (e.g. myocardial infarction or cerebral infarction) or  $\geq$  grade 3 venous thromboembolic event
  - h. Any grade posterior reversible encephalopathy syndrome (PRES)
  - i.  $\geq$  grade 3 congestive heart failure
  - j.  $\geq$  grade 2 non-gastrointestinal (GI) abscesses and fistulae;
6. Cohort 2 only: Prior progression on a bevacizumab-containing regimen (defined as having progressed/grown through bevacizumab by RANO criteria within 2 months of prior bevacizumab treatment);
7. Pathology consistent with EGFR-amplification of tumor (i.e. greater than 15% of cells exhibiting  $> 5$  copies of EGFR loci); archival tissue may be tested for EGFR status in a separate consent;
8. ANC  $\geq$  1,000 cells/ $\mu$ l, platelets  $\geq$  100,000 cells/ $\mu$ l, hemoglobin  $\geq$  9 g/dL;
9. Adequate renal function as indicated by the following:
  - a. Serum creatinine  $\leq$  1.25 times upper limit of normal or calculated creatinine clearance  $\geq$  50 ml/min;

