### 13.5.2 Other Secondary Objectives: Response Rate and Survival

Within each cohort and dose level, radiographic response rate will be estimated as the proportion of treated patients with a complete or partial response. An exact binomial confidence interval will be generated.

Kaplan-Meier curves will be generated to describe the PFS and OS experience of patients treated with Sym004 within each cohort and dose level. Progression-free survival (PFS) is defined as the time interval between initiation of protocol treatment and either disease progression or death. If the patient is alive and progression-free, PFS will be censored at the date last known alive. Overall survival (OS) is defined as the time interval between initiation of protocol treatment and death, or date of last follow-up if alive. Estimates with confidence intervals will be generated for median PFS/OS, as well as 2 month intervals for PFS for the first year (2, 4, 6, etc..) and 6 month intervals for OS for the first 2 years (6,12, 18, 24) from the time the subject goes on study.

The analyses of response rate, OS, and PFS will focus on the dose group to which the patient was originally assigned. The impact that the few patients treated initially at the 18 mg/kg dose and subsequently with 24 mg/kg will be assessed by generating analyses with and without these patients.

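### Appendix B gives opposite response calls for patients whose only enhancing disease is non-measurable, and Section 13.5.2 does not say which level of response is counted

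*Combined protocol and SAP*

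**What the plan says.** **Endpoint.** Section 13.5.2 states that "radiographic response rate will be estimated as the proportion of treated patients with a complete or partial response", by cohort and dose level, with an exact binomial interval. It cites no response criteria. The matching sentence in the synopsis (Section 3.4) refers the reader to Appendix B as a whole, and the objectives table in Section 6 describes the endpoint without the word radiographic. Under Section 13.1, everyone who received any Sym004 is in the denominator.

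**Rule allowing a complete response.** Appendix B, table K, converts lesion findings into a radiological timepoint response. Its NA* code means "No target lesions identified at baseline". The row with target NA*, non-target CR, FLAIR/T2 not worse and no new lesion returns CR.

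**Rule forbidding it.** Item N.vi opens "For patients with non-measurable disease only at baseline" and continues "Cannot have a CR or PR" and "Best response possible is SD".

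**Steroids and clinical status.** Tables L and M add steroid and clinical-status conditions to the MRI result. Item N.iii turns an MRI complete response into a partial response if the patient is still on steroids. Item N.iv reads "If PR by MRI but steroids up : SD".

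**The concern.** Two analysts who both follow the documents can count different numbers of responders from the same scans, for two separate reasons:

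- For a patient whose only enhancing disease is non-measurable, the appendix contains one rule that makes the patient a responder and another that rules this out.
- For a patient whose tumour shrinks on MRI while the steroid dose rises, the answer depends on whether response means the radiological result or the overall result. Section 13.5.2 does not say which.

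The trial is open-label and single-arm, and it reports response in small groups. If the rule is chosen after the scans have been read, the choice can follow the results.

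**Working it through.** The plan states no target or expected value for response rate, so there is no figure to reproduce. The check sets the rules side by side and then sizes one changed call.

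**1. Do table K and item N.vi cover the same patient?** Take an enhancing lesion of 12 × 8 mm, which is the appendix's own example of a non-measurable lesion (item E).

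- Item D requires two perpendicular diameters of at least 10 mm, so the lesion is not measurable and cannot be a target.
- Item H places all non-measurable lesions among the enhancing non-target lesions.
- If this is the only enhancing disease, the patient is NA* for target lesions and has a non-target lesion.

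Suppose the lesion disappears, FLAIR/T2 is not worse and nothing new appears:

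| Rule | Call | Counts in CR + PR |
|---|---|---|
| Table K, NA* with non-target CR | CR | 1 |
| Item N.vi | SD at best | 0 |

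The two groups are nearly, but not exactly, the same. Item H also lists measurable lesions not chosen as targets. Since item F tells the reader to pick the largest lesions as targets, an NA* patient with enhancing disease will normally have only non-measurable disease.

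**2. Can such a patient be enrolled?** Yes. Inclusion criterion 1 (Section 3.3) accepts a new enhancing lesion and sets no size threshold, and no other criterion asks for measurable disease. Section 13.1 keeps the patient in the denominator, so only the numerator changes.

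**3. Does choosing table L settle it?** No. Table L takes the MRI call as its first condition. A table K complete response passes through if steroids are at or below physiological levels and clinical status is stable or better. The table K and N.vi conflict needs its own repair.

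**4. Which steroid rules change the rate?**

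| MRI result | Steroids | Table K | Appendix steroid rule | Change in CR + PR count |
|---|---|---|---|---|
| CR | Continued, not above baseline | CR | PR (N.iii) | 0 |
| PR | Increased | PR | SD (N.iv) | −1 |
| CR | Above baseline | CR | PR by N.iii, but table L does not allow PR with an increased dose | 0 or −1 |

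The clinical-status condition in tables L and M can also remove a responder. Steroid use is foreseeable, because inclusion criterion 12 admits patients on a stable dose.

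**5. Size of one changed call.** Shift = 1/n. The maximum sizes at 24 mg/kg come from Section 13.8.2, and the stage 1 sizes from Section 13.7.2.

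| Cohort | Full accrual | Stopped after stage 1 |
|---|---|---|
| 1 | 1/36 = 2.8 points | 1/19 = 5.3 points |
| 2 | 1/29 = 3.4 points | 1/12 = 8.3 points |

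**6. Illustration with exact intervals.** For x responders of n, the lower limit is the α/2 quantile of Beta(x, n − x + 1) and the upper limit is the 1 − α/2 quantile of Beta(x + 1, n − x). Responder counts are assumed. The plan gives no confidence level, so α = 0.05 is also assumed.

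| Cohort | x/n | Rate | 95% interval |
|---|---|---|---|
| 1 | 2/36 | 5.6% | 0.7% to 18.7% |
| 1 | 3/36 | 8.3% | 1.8% to 22.5% |
| 2 | 1/29 | 3.4% | 0.1% to 17.8% |
| 2 | 2/29 | 6.9% | 0.8% to 22.8% |

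**The case against.** **N.vi may simply cap table K.** Table K is a radiological timepoint call, table L an overall visit call, and item N.iii to N.v each take an MRI result and give the final call. N.vi sits in that list and speaks of best response, so reading it as an override is natural. It is probably what was meant. But no sentence says so, item N is presented only as additional help, and an endpoint called radiographic points back to table K.

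**The plan does not leave out the steroid rules.** A reader might infer from the word radiographic that Section 13.5.2 disregards the downgrades, so that shrinkage under rising steroids counts as response. The documents do not support this. Section 13.5.2 gives no criteria at all, the synopsis refers to the whole of Appendix B, and Section 6 omits the word. What remains is that the level of response is not named.

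**T2/FLAIR-only entry does not create the contradiction.** Inclusion criterion 1 also accepts progression by this route ("or a significant increase in T2/FLAIR abnormality without another co-morbid cause"). A patient with no enhancing disease has neither target nor enhancing non-target lesions and falls in the table K row that returns No Change. The conflict arises only through enhancing lesions too small or too poorly defined to measure.

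**The effect is limited.** Response rate is a descriptive secondary endpoint with no hypothesis or threshold. The PFS6 stopping and decision rules do not use CR or PR. This stands and keeps the point modest.

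**Conclusion.** The contradiction between table K and item N.vi is real. It can occur under the eligibility criteria, and it changes the numerator of a reported secondary endpoint. Separately, the plan leaves open whether response is the radiological or the overall result. The two readings differ for a partial response on MRI with increased steroids and for a patient whose clinical status has worsened. Item N.iii alone cannot change the rate.

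The size is 2.8 points per patient of 36 and 3.4 per patient of 29, and more if a cohort stops after stage 1. The total effect cannot be stated, because the documents do not give the number of patients without measurable disease or with a steroid increase at response. A reader might infer that the response rate will be inflated. The table K reading can only give the same or a higher count, but nothing in the documents shows that any patient will be affected. The intervals above rest on assumed responder counts and an assumed 95% level.

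**What to change.** 1. Make one rule apply to patients without target lesions. Either correct the table K row for NA* with non-target CR, or state in Section 13.5.2 that N.vi caps table K for the response-rate endpoint. The second leaves the centre's imaging procedure untouched.
2. State in Section 13.5.2 that response is the overall visit response of table L, with items N.iii and N.iv and the confirmation at four weeks or later already required by item G. Naming the level is the essential step. Table L is preferable because it applies the appendix's own steroid and clinical-status conditions.
3. Reconcile N.iii with table L for an MRI complete response when steroids are above baseline.
4. Keep the all-treated denominator and report, by cohort and dose level, how many patients had no measurable disease at baseline.

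The cost is a few lines of wording and possibly a slightly lower response rate. No new data are needed, and the PFS6 design is unaffected.
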